13.4. Electroencephalogram

Standard EEGs [REDACTED] will be performed to monitor patients with documented or suspected seizure activity in accordance with standard of care.

13.5. Adverse and Serious Adverse Events

13.5.1. Definition of an Adverse Event

An AE is defined as any unfavorable or unintended sign (eg, including an abnormal laboratory finding), symptom, or disease temporally associated with the use of a medicinal product or procedure, whether or not considered related to the medicinal product or procedure, that occurs during the study.

Exacerbations of a chronic or intermittent pre-existing condition, including either an increase in frequency and/or intensity of the condition, are all to be considered AEs.

Abnormal test findings may be considered AEs. If an abnormal laboratory value is identified, Investigators are strongly encouraged to report a diagnosis, or a sign or symptom rather than an isolated abnormal test value. An abnormal test finding should be documented as an AE if any of the following conditions are met:

- Is associated with a sign or symptom
- Requires additional diagnostic testing (repeat tests are not considered additional testing)
- Requires a medical or surgical intervention
- Leads to a change in study dosing outside of the protocol-defined dosing or discontinuation from the study
- Or does not meet any of the defined conditions, but the Investigator or Sponsor considers the result as clinically significant or meeting the definition of an AE.

This definition also includes signs or symptoms resulting from misuse or abuse of the product from drug overdose, drug withdrawal, medication error, as well as outside what is foreseen in the protocol, such as drug interactions and extravasation.

An AE does not include the following:

- Medical or surgical procedures (eg, surgery, endoscopies, tooth extraction, and transfusion). The condition that leads to the procedure is the AE (eg, laparoscopic cholecystectomy is the procedure or treatment for an SAE of necrotic gall bladder).
- Pre-existing diseases or conditions present or detected prior to the Screening/Baseline evaluation that do not worsen
- Situations where an untoward medical occurrence has not occurred (eg, hospitalization for elective surgery, social, and/or convenience admissions)

13.5.2. Detection of Adverse Events

The Investigator is responsible for detecting, assessing, documenting, and reporting all AEs. All serious and nonserious AE information will be collected from the time informed consent is signed until study completion.

Adverse events reported by the patient and/or parent or legal guardian, and/or identified in response to an open-ended question from study personnel, or revealed by observation, physical examination, or other study procedures, must be collected and recorded as described in [Section 13.5.3](#).

13.5.3. Recording Adverse Events

All observed or volunteered AEs, regardless of causal relationship, must be recorded and reported.

For all AEs, the Investigator must obtain adequate information in order to:

- determine the AE outcome
- determine if the event meets criteria for an SAE
- assess the AE severity
- determine AE causality

Adverse events must be documented in clear, unambiguous medical terms. Study personnel are to be advised to refrain from using abbreviations or acronyms.

For each AE, record only the diagnosis on the AE page of the CRF. Do not report the characteristic signs and symptoms of the diagnosis as additional AEs.

If a diagnosis is not available, record each sign and symptom as an AE. When a diagnosis becomes available, study personnel are to update the AE page of the CRF with relevant diagnosis only.

All AEs that later increase in frequency and/or severity (medical and scientific judgment should be exercised by the Investigator) will be considered new AEs and will be recorded on a new line on the AE page or the CRF. For medical or surgical procedures (eg, surgery, endoscopy, tooth extraction, or transfusion), the condition/diagnosis leading to the procedure should be recorded as the AE (eg, laparoscopic cholecystectomy is the procedure or treatment for an SAE of necrotic gall bladder). Withdrawal due to an AE or SAE must be clearly differentiated from withdrawal due to other reasons.

Initial AEs should be closed out, with an end date consistent with the date that the AE increased in frequency and/or severity. The new AE should be recorded on a new line of the AE page, with onset date consistent with the date of increase in frequency and or severity.

13.5.4. Definition of a Serious Adverse Event

Any AE that fulfills any one of the criteria listed below must be recorded as an SAE.

An SAE or reaction is described as any untoward medical occurrence, that at any dose:

1. Results in death
2. Is life-threatening (NOTE: The term "life-threatening" in the definition of "serious" refers to an event in which the patient was at risk of death at the time of the event; it does not refer to an event which hypothetically might have caused death if it were more severe.)
3. Hospitalization or prolongation of hospitalization. (NOTE: Hospitalization requires inpatient or prolongation of an existing hospitalization. Adverse events that are associated with hospitalization or prolongation of hospitalization are considered SAEs). Hospitalization does not necessarily include the following:

- a. rehabilitation/hospice/nursing facility
- b. Emergency room/department visit less than 24 hours in duration
- c. Elective or preplanned admission/surgery
- d. Protocol-specified admission, or admission for a pre-existing condition not associated with either a new AE or with worsening of a pre-existing AE

4. Results in persistent or significant disability/incapacity
5. Is a congenital anomaly/birth defect
6. Is an important medical event

NOTE: Medical and scientific judgment should be exercised in deciding whether expedited reporting is appropriate in other situations, such as important medical events that may not be immediately life-threatening or result in death or hospitalization, but which may jeopardize the patient or may require intervention to prevent one of the other outcomes listed in the definition above. These should also usually be considered serious. Examples of such events are intensive treatment in an emergency room or at home for allergic bronchospasm; blood dyscrasias or convulsions that do not result in hospitalization; or development of drug dependency.

Severity and seriousness must be differentiated. Severity describes the intensity of an event, and both AEs and SAEs can be assessed as severe, while the term seriousness refers to an AE that has met the criteria for an SAE, as described above.

13.5.5. Severity Assessment

An assessment of severity will be made by the Investigator using the following criteria:

- Mild: events require minimal or no treatment and do not interfere with the patient's daily activities.

- Moderate: events result in a low level of inconvenience or concerns with the therapeutic measures. Moderate events may cause some interference with functioning.
- Severe: events interrupt a patient's usual daily activity and may require systemic drug therapy or other treatment. Severe events are usually incapacitating.

Changes in the severity of an AE should be documented to allow an assessment of the duration of the event at each level of intensity to be performed. Adverse events characterized as intermittent require documentation of onset and duration of each episode if the severity of the intermittent event changes.

13.5.6. Causality Assessment

An Investigator causality assessment must be provided for all AEs. This assessment must be recorded in the CRF and any additional forms, as appropriate. The definitions for the causality assessments are as follows:

- Not related (unrelated): this relationship suggests that there is no causal association between study drug and the reported event.
- Unlikely related: this relationship suggests that the clinical picture is highly consistent with a cause other than the study drug, but attribution cannot be made with absolute certainty, and a relationship between the study drug and AE cannot be excluded with complete confidence.
- Possibly related: this relationship suggests that treatment with study drug may have caused or contributed to the AE, ie, the event follows a reasonable temporal sequence from the time of drug administration, and/or follows a known response pattern to the study drug, but could also have been produced by other factors.
- Probably related: this relationship suggests that a reasonable temporal sequence of the event with study drug administration exists, and the likely causal association of the event with study drug. This will be based upon the known pharmacological action of study drug, known or previously reported adverse reactions to the study drug or class of drugs, or judgment based on the clinical experience of the Investigator.
- Definitely related: temporal relationship to the study drug. Other conditions (concurrent illness, concurrent medication reaction, or progression/expression of disease state) do not appear to explain event, which corresponds with the known pharmaceutical profile, improves with study drug discontinuation, and/or reappears with study drug rechallenge.

13.5.7. Outcome

For all AEs, regardless of causal relationships, the Investigator must follow-up on the event outcome until the event or sequelae either resolves or stabilizes.

If a patient experiences an SAE with an outcome of death:

- The SAE resulting in death should have an outcome documented as death/fatal, with an end date being the date of death.

- If the patient had additional AEs/SAEs that were ongoing at the time of death, these events would be documented as ongoing with no end date.
- Only one event should have an outcome of death/fatal, unless an autopsy report or Investigator states otherwise.

13.5.8. Reporting Adverse Events and Serious Adverse Events to Sponsor

All nonserious AEs must be recorded on the CRF upon awareness.

All AEs must be assessed by the Investigator to determine if they meet criteria for an SAE. All SAEs must be reported to the Sponsor or designee immediately or within 24 hours of the Investigator or staff becoming aware of the events. The Investigator must complete, sign, and date the email cover page, complete the SAE CRF pages, verify accuracy of the information recorded on the SAE pages with the corresponding source documents, and send a copy via email to the contact information provided [REDACTED]
[REDACTED]

Additional follow-up information, if required or available, should be entered into the CRF, and sent to Sponsor within 24 hours of the Investigator site or staff becoming aware of this additional information, via the reporting process outlined above. These reporting timelines need to be followed for all initial SAE cases and follow-up versions of the initial cases.

All SAEs will be recorded from the time the ICF is signed until 30 days following study completion.

For all SAEs, the Investigator must provide the following:

- Clear identification of the Investigator/Reporter with full contact information, country and site number
- Subject identification details (subject's unique study identification number)
- Investigational Medicinal Product(s) administration details (dose and dates)
- Seriousness criteria
- appropriate and requested follow-up information in the time frame detailed above
- causality of the serious events
- outcome of the serious events
- medical records and laboratory/diagnostic information

13.5.9. Sponsor Reporting Requirements

The Sponsor or its legal representative is responsible for notifying the relevant regulatory authorities of SAEs meeting the reporting criteria. This protocol will use the current Investigator Brochure as the Reference Safety document. Serious adverse event expectedness and reporting criteria will be determined by the Sponsor from the Reference Safety document.

13.5.10. Investigator Reporting Requirements

The Investigator must fulfill all local regulatory obligations required for the study Investigators. It is the Investigator's responsibility to notify the IRB/EC of all SAEs that occur at his/her site. Investigators also will be notified of all unexpected, serious, drug-related events that occur during the study. Each site is responsible for notifying its IRB/EC of these additional SAEs.

14. STATISTICAL METHODS AND PLANNED ANALYSES

Assessments will be binned into analysis visits in such a way that the assessment closest to the target study day among all assessments observed within a window around the target day will be designated for analyses over time. The visit windows will span from above the midpoint of the target day and prior visit target day up to and including the midpoint between the target day and next visit target day.

All data collected during the study will be presented in data listings, tables, and figures as described below. Continuous variables will be summarized using mean, SD, median, minimum, and maximum. Categorical variables will be summarized using percentages and frequency distributions. Confidence intervals will be provided for all means and percentages to aid in interpretation.

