4.3.6. Vital Signs

Vital sign assessments will include blood pressure, heart rate, respiratory rate, and temperature.

Additional systolic and diastolic blood pressure measurements are to be collected [REDACTED] [REDACTED] at approximately 30, 60, 90, and 120 minutes post-EOI and at 6 and 12 hours post-EOI.

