13.2. Vital Signs

[REDACTED] At all outpatient study visits, the vital sign measurement to be recorded in the CRF is the first set of vital signs taken.

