14.8.2. Laboratory Parameters

Incidence of abnormalities for clinical laboratory assessments (chemistry and hematology) will be summarized by visit. Laboratory analytes and their changes from baseline will be summarized by visit.

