14.8.3. Physical Examinations and Vital Signs

Adverse physical examination changes will be reported as AEs and analyzed as such. Vital signs and their changes from baseline will be summarized by visit.

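### The by-visit laboratory and vital-sign tables use one value per window, with no any-time or worst-value summary and no time-point summary of post-infusion blood pressure

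*Combined protocol and SAP*

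**What the plan says.** Section 14 sets one rule for assigning assessments to visits in longitudinal analyses: "the assessment closest to the target study day among all assessments observed within a window around the target day will be designated for analyses". Each window opens just after the midpoint with the previous target and runs "up to and including the midpoint between the target day and next visit target day". The rule makes no exception for safety data.

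Section 14.8.2 gives the laboratory summaries: "Incidence of abnormalities for clinical laboratory assessments (chemistry and hematology) will be summarized by visit", and "Laboratory analytes and their changes from baseline will be summarized by visit". The statistical methods in the Synopsis also report the incidence of laboratory abnormalities by visit. Section 14.8.3 does the same for vital signs: "Vital signs and their changes from baseline will be summarized by visit".

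Two kinds of safety data fit poorly into one value per visit:

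- **Unscheduled laboratory samples.** Section 13.3 requires blood and urine samples seven days after an unscheduled dose adjustment.
- **Post-infusion blood pressure.** Section 4.3.6 requires extra systolic and diastolic readings "at approximately 30, 60, 90, and 120 minutes post-EOI and at 6 and 12 hours post-EOI". Table 10, footnote c, repeats this. The days on which the series is taken are redacted.

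Section 3.2 names changes in vital signs and safety laboratory tests as safety endpoints alongside adverse events.

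**The concern.** A closest-to-target rule suits a trend table, where each patient should contribute one value per visit. It suits an incidence table less well, because the question there is whether a patient ever had an abnormal value. Samples taken around a dose change or a clinical event tend to lie off the target day, so they tend to lose to a routine sample nearer to it. If the routine value is normal, the patient counts as normal at that visit.

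A series of readings from 30 minutes to 12 hours after infusion is useful mainly for showing change over those hours. A by-visit change from study baseline cannot show that: it mixes any infusion effect with growth and elapsed time. The readable plan describes no other summary of the series.

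At stake is whether the summaries for two named safety endpoints reflect all the data collected for them.

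**Working it through.** The plan gives no figure on this point, so there is none to reproduce. The check applies the Section 14 rule to the planned samples and readings.

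**Inputs from the documents**
- One value per window, closest to target; windows run from midpoint to midpoint (Section 14).
- Laboratory follow-up seven days after an unscheduled dose adjustment (Section 13.3).
- Six post-infusion readings, each systolic and diastolic (Section 4.3.6).

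**Assumptions** (the visit schedule is redacted)
- Consecutive laboratory targets at Day 28 and Month 3, with Month 3 as Day 84, 90 or 91.
- One routine pre-infusion reading on a series day.
- A probability p of 5% to 20% that a sample is abnormal, independent between samples.

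**1. Where an unscheduled sample falls.** With Month 3 as Day 90, the midpoint is (28 + 90)/2 = 59. An unscheduled adjustment on Day 40 puts the follow-up sample on Day 40 + 7 = 47. Since 47 ≤ 59, it belongs to the Day 28 visit, at a distance of 47 − 28 = 19 days. Any sample less than 19 days from Day 28 displaces it. With Month 3 as Day 84 or 91, the midpoint is 56 or 59.5 and the result is the same.

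The loss is not automatic. If the Day 47 sample is the only one in the window, or the closest, it is the value tabulated.

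**2. What the incidence table can miss.** The chance of at least one abnormal value among k samples in a window is 1 − (1 − p)^k. With one designated value it is p.

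| Samples in window (k) | p = 5% | p = 20% |
|---|---|---|
| 1 (the designated value) | 5% | 20% |
| 2 | 1 − 0.95² = 9.8% | 1 − 0.80² = 36% |
| 3 | 1 − 0.95³ = 14.3% | 1 − 0.80³ = 48.8% |

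This shows direction and order of size only. Repeat samples from one child are not independent, and positive correlation would narrow the gap. The comparison applies only to patients with extra samples in a window.

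**3. Weight of one patient.** Section 14.1 sets no sample size. If 5 to 20 patients are analysed (assumed), one patient moves an incidence by 1/5 = 20 to 1/20 = 5 percentage points.

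**4. Blood pressure.** Six time points × 2 pressures = 12 post-infusion values per series day. With one pre-infusion reading there are 7 readings. The readings up to two hours, and usually those at 6 and 12 hours, share a study day with the pre-infusion reading. They are therefore equally far from the target day, and Section 14 has no rule for ties. At most 1 of 7 readings is designated, so at least 6/7 = 86% are not, and the plan does not say which one is kept.

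**The case against.** The strongest reply is that the by-visit tables are not the main route by which harm is reported.

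- **Adverse event tables.** Section 13.5.1 makes an abnormal finding an adverse event if it comes with a sign or symptom, needs further diagnostic work or an intervention, changes dosing outside the protocol or leads to discontinuation, or is judged clinically significant. Section 14.8.1 tabulates treatment-emergent events from first dose, with no visit window. Samples taken around an event or a dose change are the most likely to qualify.
- **Listings and oversight.** Section 14 also puts all collected data into listings, tables and figures. The Safety Review Committee and Data Monitoring Committee review individual patients' data.
- **Scope of the rule.** It chooses a value for analyses over time. It does not delete data.

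All of this stands, and it limits the point. A reader might infer that unscheduled abnormalities and post-infusion readings disappear from the safety reporting altogether. The documents do not support that. Nor is every off-schedule sample lost when a scheduled one exists: visits have their own windows (Tables 10 and 11), so an unscheduled sample can be the closer one.

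The reply does not cover abnormal values that are not recorded as adverse events. Several of the Section 13.5.1 conditions turn on investigator judgment, a repeat test does not count as additional testing, and investigators are steered towards a diagnosis rather than an isolated value. Listings show values but give no incidence and no change after infusion.

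A second tempting inference is that Section 13.2, "At all outpatient study visits, the vital sign measurement to be recorded in the CRF is the first set of vital signs taken", contradicts Section 4.3, which has all assessment results recorded in the case report form. That is not shown. The series days and the text just before the Section 13.2 sentence are redacted, and Table 10 lists vital signs and additional blood pressure measurements as separate rows. The first-set rule can be read as covering routine vital signs only.

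**Conclusion.** The point holds in a limited form. Applied as written, the Section 14 rule leaves an abnormal unscheduled laboratory value out of the Section 14.8.2 incidence table whenever another sample in the window is closer to target. No any-time or worst-value summary in the readable text recovers it. The table can therefore understate incidence, chiefly for abnormalities not recorded as adverse events.

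For blood pressure, the window rule does not itself exclude the post-infusion readings. The gap is a missing tie-break and the lack of any described summary by time point for a series of 12 values per series day.

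The size cannot be fixed from the documents. The percentages above rest on assumed target days, an assumed abnormality rate and independence. The visit schedule and parts of Sections 13.2 and 14.8.1 are redacted, so a provision in hidden text cannot be ruled out; the Section 14 visit rule and the wording of 14.8.2 and 14.8.3 are readable. This is a gap in the planned summaries, not a failure of safety monitoring, and the data needed to close it are already collected.

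**What to change.** - **Section 14:** limit the closest-value rule to by-visit trend tables and state a tie-break for readings taken on the same day.
- **Section 14.8.2:** keep the by-visit tables. Add the incidence of chemistry and hematology abnormalities at any time after first dose, using each patient's worst value from all scheduled and unscheduled samples.
- **Section 14.8.3:** summarise the additional blood pressure series by time after end of infusion, as change from the same-day pre-infusion reading where one was taken. Report the largest fall and largest rise per patient.
- **Section 13.2:** clarify, if that is the intention, that the first-set rule covers routine vital signs and that every reading of the additional series is recorded with its time.

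The cost is a few lines of wording and two extra tables, with no new procedure for the patients. The drawback is that worst-value incidence will be somewhat higher in patients sampled more often, so the number of samples per patient should be shown beside it.

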14.1. Determination of Sample Size

There will be no minimum or maximum number of patients for this study. The final sample size and determination of study success relative to efficacy will depend on the OS rate as each successive patient reaches study completion.

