Eligible patients beyond the neonatal period with genetically confirmed evidence of MoCD Type A, a biochemical profile, and clinical picture consistent with MoCD Type A may also be enrolled following completion of Screening/Baseline assessments. Data from procedures conducted as part of standard of care prior to study participation may be collected as part of Medical History. Genetic confirmation of the diagnosis of MoCD Type A may be obtained after initiation of ORGN001 therapy in certain cases.

In all patients, ORGN001 will be administered daily from Day 1 of the study. Completion of a brain MRI may be delayed until after the initiation of ORGN001 if not feasible to complete prior to study drug initiation. [REDACTED]

[REDACTED] patients will continue to receive daily infusions of ORGN001 at home [REDACTED]

[REDACTED] and will return to the clinic for study visits for safety, efficacy, and PK assessments.

A Safety Review Committee (SRC) and an external, independent Data Monitoring Committee (DMC) will review safety, efficacy, and PK data for this study periodically and will be consulted on an ad hoc basis for individual cases. Continuation of ORGN001 treatment will be based on treating physician assessment as well as recommendations by the combined SRC and DMC regarding the benefit: risk assessment for each patient. [REDACTED]

Patients with a genetic diagnosis other than MoCD Type A will be discontinued from ORGN001 treatment as they are not expected to receive any treatment benefit. Patients who discontinue prematurely from treatment will be followed for 28 days, [REDACTED].

Dose Selection Strategy: A population PK (PopPK)-based approach has been utilized to create a dosing scheme that targets the higher end of the originally acceptable exposure range for ORGN001 (no observable adverse effect level [NOAEL]: AUC [REDACTED] at the highest dose studied in the original toxicology study that was limited by solubility issue. Since then, higher doses have been studied and were all well tolerated in rats and dogs using an improved IV formulation. [REDACTED]

A PopPK model was derived to characterize ORGN001 clinical PK in healthy adult volunteers (Study ALXN1101-MCD-101) and children with MoCD Type A (Study ALXN1101-MCD-201). Due to [REDACTED] renal clearance of ORGN001 in adults (Study ALXN1101-MCD-101), a function was included to account for the expected impact of [REDACTED]

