6.2. Data Monitoring Committee

[figure not shown]
[REDACTED] The DMC will have access to all safety data, in accordance with its primary function of ensuring patient safety. The DMC may make

recommendations to the Sponsor regarding safety issues, study conduct, and/or modifying, extending, or stopping the study.

The DMC will review each patient's record [REDACTED], prior to any study dose escalation [REDACTED]

[REDACTED]. The SRC may request additional ad hoc DMC meetings, as needed.

Each member of the DMC will be required to sign a contract agreement, including confidentiality and financial disclosure statements, assuring no conflicts of interest, as a condition for membership on the committee.

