7.2. Patient Inclusion Criteria

Patients must meet all of the inclusion criteria to be considered eligible for enrollment in this study.

- Male or female neonatal patients (1 to 28 days of age [inclusive] at the time of ORGN001 administration, with day 1 of age corresponding to the day of birth), or infant (29 days to < 2 years of age) or child (2 to 5 years of age [inclusive]) with MoCD Type A, previously untreated with ORGN001 or treated with ORGN001 through the EAP
- In neonates, diagnosis of MoCD Type A, based on:
 - Prenatal genetic diagnosis, or
 - Onset of clinical and/or laboratory signs and symptoms consistent with MoCD Type A (eg, seizures, exaggerated startle response, high-pitched cry, axial hypotonia, limb hypertonia, feeding difficulties, elevated urinary sulfite and/or SSC, elevated xanthine in urine or blood, or low or absent uric acid in the urine or blood) within the first 28 days after birth
- In infants or children, diagnosis of MoCD Type A, based on:

- Confirmed genetic diagnosis (genetic confirmation of the diagnosis of MoCD Type A may be obtained after initiation of ORGN001 therapy in certain cases), biochemical profile, and clinical presentation consistent with MoCD Type A
- Parent or legal guardian must have signed the ICF prior to any study procedures being performed

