14.5. Patient Disposition and Extent of Exposure

The number of patients screened, treated, continuing treatment after confirmation of enrollment criteria, and completing the 12-month and 36-month study periods will be tabulated. Reasons for any patient withdrawals will be provided. The number of patients in the safety and efficacy analysis sets, along with reasons for exclusion from analysis sets, will be tabulated.

Extent of exposure with ORGN001 will be summarized among both the Safety Set and FAS, with respect to number of infusions, number of missed and partial infusions, and duration of treatment period.

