14.7.1. Use of Natural History Study ALX-MCD-502

Data from natural history study ALX-MCD-502 will be used to support the current study in order to guide interpretation by representing the expected clinical time course for patients with MoCD Type A in the absence of ORGN001 treatment.

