14.7.2. Primary Efficacy Analysis

The primary efficacy analysis will summarize OS, defined as the interval in months from the date of birth to the date of death or date last known alive (patients still on study will be censored at the data cutoff date), whichever occurs first.

The analysis of OS will be based on the Kaplan-Meier methodology for estimation of survival parameters. The median duration of OS will be estimated based on the 50th percentile of the Kaplan-Meier distribution; additional summary statistics, including the 25th and 75th percentiles, 95% confidence intervals (CIs) on the median and the other percentiles and proportion of censored patients. The analysis of OS will be done using the FAS, the NmFAS, and the PmFAS.

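### Section 14.1 lets sample size and study success follow an undefined running OS rate, and the FAS Kaplan-Meier curve from birth in Section 14.7.2 credits survival before study entry

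*Combined protocol and SAP*

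**What the plan says.** **Sample size and success.** Section 4.2 sets no minimum or maximum number of patients. Section 14.1 repeats this and adds: "The final sample size and determination of study success relative to efficacy will depend on the OS rate as each successive patient" completes the study. It says nothing more about sample size or success.

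**Completion.** Section 14.5 counts patients "completing the 12-month and 36-month study periods will be tabulated". Section 6.3 allows treatment to continue beyond Month 36.

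**Primary analysis.** Section 14.7.2 takes OS as "defined as the interval in months from the date of birth to the date of death or date last known alive". It estimates OS by Kaplan-Meier in the FAS, NmFAS and PmFAS, reporting the median, the quartiles and "95% confidence intervals (CIs) on the median and the other percentiles and proportion of censored patients". The list is not closed, but it names no survival probability at a stated age and no adjustment for age at entry.

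**Who enters.** The FAS (Section 14.2) has no age limit. Section 7.2 admits neonates, infants and a "child (2 to 5 years of age [inclusive]) with MoCD Type A, previously untreated with ORGN001 or treated with ORGN001 through the EAP".

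**Comparator.** Section 14.7.1 says that data from ALX-MCD-502 "will be used to support the current study in order to guide interpretation".

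**Visibility of outcomes.** The study is open-label. Under the Synopsis (Methodology), the two committees "will review safety, efficacy, and PK data for this study periodically". Section 6.2 lets the DMC make "recommendations to the Sponsor regarding safety issues, study conduct, and/or modifying, extending, or stopping the study".

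**The concern.** There are two separate problems.

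First, Section 14.1 makes both N and the verdict on efficacy depend on a quantity that is not defined. Nothing visible says at what age the rate is read, what value counts as success, or against what. Because deaths are known as they occur, the age, the benchmark and the moment of closing enrolment could all be settled after the result is visible.

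Second, the FAS mixes children followed almost from birth with children who had to be alive at a later age to enrol. Ordinary Kaplan-Meier from birth places the second group in the risk set over months in which their deaths could not have been recorded. The curve is pushed upward, and it will be read beside an untreated natural history. The primary estimate would then favour the drug for a reason unrelated to the drug.

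**Working it through.** The plan states no N, event count, null rate, alpha or threshold, so there is no figure of its own to reproduce. The first check is textual; the others are illustrations.

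**1. Is the OS rate pinned down?** Section 14.1 gives no age, Section 14.5 gives two completion milestones, Section 6.3 allows continuation past both, Section 14.7.2 lists percentiles and no rate, and Section 14.7.1 sets no benchmark. None of them defines it. Sections 14.1, 14.7.1 and 14.7.2 show no redaction marker.

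**2. Does the age matter?** Input: the median survival of 3 years for MoCD in Section 2.3 (all types). Assumption: exponential survival, S(t) = 0.5^(HR × t/36).

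| | 12 months | 36 months |
|---|---|---|
| HR 1 | 0.5^(12/36) = 79% | 50% |
| HR 0.5 | 0.5^(6/36) = 89% | 0.5^0.5 = 71% |

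**3. Credit for survival before entry.** Further assumptions: no drug effect, neonates entering uniformly over days 0 to 28, late entrants uniformly at 1 to 72 months, and 36 months of follow-up after entry. Nobody is then censored before 36 months of age, so the unadjusted estimate at 36 months is simply the proportion alive.

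- A late entrant at age a < 36 is alive at 36 months with probability 0.5^((36 − a)/36). With λ = ln 2/36 = 0.01925, the average over a = 1 to 36 is (1 − 0.5^(35/36))/(35λ) = 0.490/0.674 = 0.728.
- A late entrant at a ≥ 36 counts as alive with certainty.
- All late entrants: (36/71) × 1 + (35/71) × 0.728 = 0.866.
- Neonates: about 0.504.
- 25% late: 0.25 × 0.866 + 0.75 × 0.504 = 0.595. 50% late: 0.685.

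A simulation of 200,000 patients gave 0.593 and 0.684. The true value is 0.500, and Kaplan-Meier with delayed entry returned about 0.50 in both mixes. With neonates only, the unadjusted value was 0.504, so the effect there is negligible.

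**4. What delayed entry costs and where it fails** (6,000 simulated trials per setting).

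- n = 10, half late: SD about 0.20 against 0.14 unadjusted, but root-mean-square error 0.20 against 0.23.
- n = 20, 25% late: root-mean-square error 0.12 against 0.14.
- Late presenters with half the hazard, n = 20 (Section 2.1 says they may progress more slowly): unadjusted 61% or 71%, delayed entry 52% or 54%. Most of the excess goes, but not all.
- Late entrants only, n = 10: delayed entry averages 58% with SD 0.33, and is exactly 0% in 13% of runs. It should not be used there.

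**5. Will the planned median exist?** With all patients entering near birth and followed for 36 months at HR 0.5, each dies by 36 months with probability 1 − 0.707 = 0.293. The binomial probability that at least half die is 15%, 14% or 4% for n = 5, 10 or 15. At HR 0.25 it is 3%, 1.3% or 0.1%. The more the drug helps, the less often the headline statistic can be estimated.

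**The case against.** **An ultra-rare disease cannot support a fixed N.** True, and none is asked for. Not fixing N differs from letting N depend on the observed endpoint.

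**The analysis is only descriptive.** Section 14.7.2 does read that way, with no test and no null. But Section 14.1 speaks of determining study success, and both statements stand in the current text.

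**OS is also planned in the NmFAS and PmFAS, and birth is the natural time scale for an inborn disease.** Both points stand. If the NmFAS means neonates at first dose, its pre-entry credit is at most 28 days. The fault lies in the FAS risk set, not in the choice of birth as origin.

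**The survival model is crude.** This stands. An exponential curve with a 36-month median puts only 1 − 0.5^(1/36) = 1.9% of deaths in the first month, whereas Section 2.3 says that neonatal death is common. The late-entry shares and ages have no source in the documents.

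**Redaction may hide more.** This stands in part. The NmFAS and PmFAS definitions and parts of Sections 3.2, 14.3 and 14.7.3 are blacked out or missing, so a fixed-age or sensitivity analysis there cannot be excluded.

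**Stronger readings to avoid.** A reader might infer an inflated type I error. Under an assumed exact one-sided 0.025 test of a 50% null after every completer, false success by n = 20 is 5.3%, against 2.1% for one look. But the plan states no test, null, cap or number of looks, so these figures describe an assumed rule only. Nor do the documents show that the sponsor means to stop on a favourable result. The abbreviation list has an objective performance criterion and the references include a paper on prior probabilities, but the visible text uses neither, so no hidden success rule should be read from them.

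**Conclusion.** The point holds, limited to Section 14.1 and to the FAS analysis in Section 14.7.2. It should be fixed.

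That the OS rate, its age, its threshold and its comparator are undefined follows from the text alone. So does the upward direction of the unadjusted FAS curve: it needs only some late entrants and some mortality before their entry. Prior expanded access treatment does not change this, because those children too had to be alive to enrol.

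The size is illustrative. About 9 or 18 percentage points at 36 months (59% or 68% against 50%) rests on exponential survival, assumed entry ages of 1 to 72 months, late shares of 25% or 50%, and full 36-month follow-up. The documents do not support quoting these as expected biases, nor saying that no other analysis of survival is planned anywhere.

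**What to change.** **(a) Section 14.7.2.** Keep birth as the time scale, but let each FAS patient enter the risk set at the age of first dose in this study. Show numbers at risk, with the planned unadjusted FAS and NmFAS curves alongside. State that the estimate is unreliable where few are at risk at early ages. For any set made up only of late entrants, report survival from first dose descriptively. Keep the percentiles and add Kaplan-Meier survival probabilities at named ages (for example 12 and 36 months). Their 95% CIs should suit small samples and exist with zero deaths: with m at risk throughout and no deaths, the exact lower limit is 0.025^(1/m), which is 69% for m = 10 and 48% for m = 5.

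**(b) Section 14.1.** Replace the second sentence with, for example: Enrolment closure and the efficacy data cut-off will be set in advance and not on the basis of observed OS, apart from DMC recommendations under Section 6.2; one primary efficacy analysis will be done at that cut-off.

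**(c) Success.** Either fix, before the cut-off, a criterion at a named age against ALX-MCD-502 that allows for the sampling error of both studies, or delete the success wording and call the efficacy analysis descriptive.

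**Cost.** Protocol and SAP wording only, with no extra patients or visits and the FAS still the main population. Delayed-entry estimates are less precise (SD about 0.20 against 0.14 at n = 10 with half entering late), and the sponsor gives up stopping on observed OS.
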